## **6.8 Coronavirus 2019 (COVID-19) Measures**

The study will be initiated while the COVID-19 pandemic is ongoing. Testing for SARS-CoV-2 is not required for this study and Investigators should follow local guidance. Should a study participant become infected with SARS-CoV-2 / contract or become suspected to have contracted COVID-19, standards for testing and management should be followed according to local and site-specific guidelines.

SARS-CoV-2 infection (if asymptomatic), COVID-19 (including pneumonia related to COVID-19), and COVID-19-related symptoms, will be reported as adverse events.

[figure not shown]
Treatments used for COVID-19 as well as vaccines are allowed without restriction during the study. They will be reported in the eCRF in the same way as any other concomitant medications described in Section 6.6 of the protocol.

The study design minimizes the physical contacts and therefore the associated risks of infection by the SARS-CoV-2. The scheduled study follow-up contacts will be performed as virtual visits and resupply of study treatment may be performed via shipment to

patient's home, when locally allowed and if feasible. The only mandatory hospital visits are those where laboratory tests for safety are required per protocol.

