### **5.3 Exclusion Criteria**

Patients meeting any of the following criteria will be excluded from the study:

1. Diagnosis of pericarditis that is secondary to specific prohibited etiologies, including tuberculosis (TB); neoplastic, purulent, or radiation etiologies; post-thoracic blunt trauma (e.g., motor vehicle accident); myocarditis
2. Estimated glomerular filtration rate (eGFR) <30 mL/min
3. Elevated alanine aminotransferase (ALT) or aspartate aminotransferase (AST) > 5 times the upper limit of normal (ULN) or ALT or AST >3x ULN plus bilirubin >2x ULN
4. Sepsis, defined as documented bacteremia at the time of screening or other documented active infection
5. Prior history of sustained ventricular arrhythmias
6. History of QT interval prolongation
7. QTc interval > 500 msec (please refer to Section 9.2.3 for bundle branch block, bifascicular block and paced rhythm correction)
8. Current participation in any research study involving investigational drugs or device
9. Inability or unwillingness to give informed consent
10. Ongoing drug or alcohol abuse
11. On any cannabinoid during the past month
12. Women who are pregnant or breastfeeding
13. Current diagnosis of cancer, with the exception of non-melanoma skin cancer
14. Any factor, which would make it unlikely that the patient can comply with the study procedures
15. Showing suicidal tendency as per the C-SSRS, administered at screening
16. On digoxin and/or type 1 or 3 antiarrhythmics
17. On immunosuppressive therapy with any of the following:
  - a. Rilonacept
  - b. Anakinra
  - c. Canakinumab
  - d. Methotrexate
  - e. Azathioprine
  - f. Cyclosporine
  - g. IVIG

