## **6.6 Concomitant Treatments**

Patients must be on SOC treatments for pericarditis with either NSAIDs, colchicine, or corticosteroids (in any combination) for at least 72 hours prior to Day 1. Unless contraindicated, these SOC treatments will be weaned during the 18 weeks EP as follows:

NSAIDs will be weaned within 2 weeks after the EP entry and corticosteroids within 6 weeks of EP entry (by 5 mg prednisone or equivalent every week).

For patients not taking corticosteroids, colchicine will be weaned between 2 and 4 weeks of EP entry, and for those on corticosteroids, colchicine weaning will be between 6 and 8 weeks of EP entry. Should it become evident that weaning of colchicine leads to high levels of pericarditis recurrence, the study leadership and the sponsor may decide colchicine weaning will no longer be performed during the EP.

Patients will not be allowed to be on immunosuppressive therapy with rilonacept, anakinra, canakinumab, methotrexate, azathioprine, cyclosporine, mycophenolate and/or IVIG and cannot take any cannabinoids during the study period nor strong inducers of CYP3A4 and CYP2C19 (see Section 17.7).

Use of digoxin and/or type 1 or 3 antiarrhythmics is an exclusion criterion for the trial. No drugs that are known to prolong QTc intervals should be started during the study (Appendix 17.6).

Also, because CardiolRx™ is known to inhibit the metabolism of certain other drugs, new symptoms or findings may represent toxicity from a concomitant medication that

had previously been well tolerated. Please refer to Section 6.3 of the Investigator Brochure (IB) and to Appendix 17.8.

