## **6.7 Management of Pericarditis Recurrence During the Extension Period**

Pericarditis recurrence during the extension period is defined as the recurrence of typical pericarditis pain associated with supportive objective evidence of pericarditis in the opinion of the investigator. At any timepoint during the EP, patients who experience suspected recurrence of their pericarditis will have been instructed to inform their site Investigator as soon as possible. Patients who experience a suspected recurrence of pericarditis symptoms will be requested to report to the study site/clinic for a scheduled or unscheduled visit, during which clinical assessments will be performed to gather all the necessary diagnostic data to confirm or rule out the presence of pericarditis recurrence. The Investigator will evaluate all assessments performed for a diagnostic workup, whether at the study site or at locations outside.

Following communication with the study medical monitor, patients who report at least 1 day with pericarditis pain measurement  $\geq 4$  on the 11-point NRS **AND** have a CRP value  $\geq 1$  mg/dL (either on the same day or separated by no more than 7 days) during the EP of the trial will receive rescue therapy at the discretion of the investigator, i.e., if not already taking; analgesics first, then NSAIDs, and then colchicine. Immunosuppressive therapy such as corticosteroids or rilonacept may be added for pericarditis recurrence at the discretion of the investigator.

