#### **9.2.11.5 Drug-Drug Interactions**

CardiolRx™ is known to be metabolized largely through the cytochrome P450 enzyme system in the liver. A number of the drugs commonly used in the management of heart failure and other CV or concomitant conditions are also capable of being inducers or inhibitors of these enzymes. The patients should specifically be monitored for (S)AEs that might reflect Drug-Drug Interactions (DDIs). See Section 6.3 of the IB for more detailed discussion.

Drugs that are known to prolong QTc intervals must not be started during the study (Appendix 17.6).

In addition, to aid investigators in screening concomitant medications for risk of DDIs, a table of medications that serve as substrate for certain enzyme isoforms inhibited by CardiolRx™ has been prepared (Appendix 17.8).

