## **17.8 Cannabidiol and Drug-Drug Interactions**

Notes:

1. Cannabidiol is a strong inhibitor of a number of CYP and UGT isoforms. Medications that depend on one (or more) of these enzyme isoforms for metabolism (that is, medications serve as a substrate for the enzyme) may then have slowed metabolism, thereby resulting in increased blood levels of the drug. For some drugs (particularly those with a narrow therapeutic index), this may result in toxicity.
2. The drugs listed are those that serve as a substrate for one or more of CYP2C8, CYP2C9, CYP2C19, CYP1A2, CYP2B6, UGT1A9 and UGT2B7.
3. Please note that certain drugs that are substrates for these enzymes are also strong inducers of CYP3A4 and therefore are exclusion criteria for this study, as depicted in Appendix 17.7.
4. Drugs listed in the table are arranged as follows: cardiovascular drugs, diabetes care drugs and then other commonly used drugs (in alphabetical order). The CYP or UGT isoform for which the drugs serve as a substrate are listed in the final column.
5. Many drugs serve as a substrate for more than one CYP or UGT isoform. They have only been recorded once in the table.
6. This patient population maybe taking a wide spectrum of medication. If a medication of interest is not included in this list, please refer to a respected website such as DrugBank ([www.drugbank.ca](http://www.drugbank.ca)) to determine likelihood of drug-drug interaction.

Drug Class	Drug Name	Signs/Monitoring/Mitigation Strategies	Enzyme
Cardiovascular Drugs			
Diuretic	Torasemide	May cause hypotension, hypokalemia, increased creatinine - Monitor body weight and renal function. Adjust dose accordingly	CYP2C8
	Triamterene	May cause hyperkalemia, hyponatremia, nausea and vomiting, diarrhea, kidney stones – monitor potassium, adjust dose or change to other diuretic	CYP1A2
Statin			
	Cerivastatin	May cause muscle breakdown, muscle pain, Monitor cholesterol level and review adverse effect profile - Adjust dose or substitute another agent	CYP2C8
	Atorvastatin		
	Fluvastatin		
	Imvastatin		
	Pitavastatin		
	Lovastatin		
	Rosuvastatin	As above. Rarely causes memory loss/confusion	CYP2C9
	Simvastatin	May cause muscle damage – adjust dose or substitute other medication	CYP2C19
Other Cholesterol lowering agents			
	Ezetimibe	Usually used in combination with a statin. May cause joint pain, muscle breakdown, diarrhea, increased upper respiratory tract infections –	UGT1A9

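### Section 6.8 lifts all limits on COVID-19 treatments that Section 6.6 bars on safety grounds, and the exclusion criteria do not match the on-study prohibitions

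*Protocol*

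**What the plan says.** **COVID-19 treatments.** Protocol Section 6.8: "Treatments used for COVID-19 as well as vaccines are allowed without restriction during the study". The next sentence supplies the section's only link to Section 6.6: "They will be reported in the eCRF in the same way as any other concomitant medications described in Section 6.6 of the protocol".

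**QT-prolonging drugs.** Section 6.6: "No drugs that are known to prolong QTc intervals should be started during the study (Appendix 17.6"). Section 9.2.11.5 repeats this in stronger terms: "Drugs that are known to prolong QTc intervals must not be started during the study (Appendix 17.6"). The synopsis row on concomitant treatments carries the same bar.

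**Immunosuppressants and inducers.** Section 6.6: "Patients will not be allowed to be on immunosuppressive therapy with rilonacept, anakinra, canakinumab, methotrexate, azathioprine, cyclosporine, mycophenolate and/or IVIG". The same sentence bars strong inducers of CYP3A4 and CYP2C19 and points to Appendix 17.7. The synopsis row agrees on both.

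**Eligibility.** Exclusion 17 reads "On immunosuppressive therapy with any of the following" and then lists seven agents, lettered a to g. The list is identical in the synopsis, Section 5.3 and SAP Section 4.2. Appendix 17.8 note 3 says that certain substrate drugs "are also strong inducers of CYP3A4 and therefore are exclusion criteria for this study, as depicted in Appendix 17.7".

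**Rescue.** Section 6.7: "Immunosuppressive therapy such as corticosteroids or rilonacept may be added for pericarditis recurrence at the discretion of the investigator".

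**The concern.** QT prolongation is a risk that this protocol watches closely. Under Section 9.2.3, a QTc of 500 msec or more, or a rise of 60 msec or more from baseline on any one measurement, is an SAE and ends study medication. The bar on starting QT-prolonging drugs protects patients and keeps such events interpretable. If a drug of that kind is started under 6.8, a later rise still triggers the stopping rule, but its attribution to study drug becomes unclear.

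The eligibility mismatch raises a related problem. A site that screens on Section 5.3 alone can enrol a patient whose established medicine is prohibited once treatment starts. It must then choose between a protocol breach and a change to that medicine after enrolment.

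There is also a reporting consequence. SAP Section 8.1 counts deviations and splits them into important and non-important. The documents do not settle whether a drug that 6.8 permits and 6.6 bars is a deviation at all.

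**Working it through.** No arithmetic beyond counting applies. The check sets the rules side by side.

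| Drug group | Section 6.6 and synopsis (concomitant treatments) | Section 9.2.11.5 | Exclusion criteria (synopsis, Section 5.3, SAP 4.2) | Section 6.8, if given for COVID-19 |
|---|---|---|---|---|
| QT-prolonging drugs | Not to be started on study | Not to be started on study | Criterion 16 only: digoxin, type 1 or 3 antiarrhythmics | No restriction |
| Strong CYP3A4/CYP2C19 inducers | Barred | No bar; monitor for interactions | Named in 0 of 17 | No restriction |
| Named immunosuppressants | Eight barred | Not mentioned | Seven listed | No restriction |

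**Step 1: 6.8 against 6.6.** Section 6.8 makes no exception for drugs barred elsewhere, and Section 6.6 makes no exception for COVID-19. The cross-reference in 6.8 says how to record the drugs, not whether they are allowed. For management of the infection, 6.8 points to local and site-specific guidelines, which adds no limit from the protocol. Any drug covered by a 6.6 bar and given for COVID-19 is permitted by one section and prohibited by the other. This needs no named drug. Nor does it depend on which of the three risk classes in Appendix 17.6 the QT bar is meant to cover, since 6.8 withholds none of them.

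**Step 2: immunosuppressant lists.**
- Section 6.6: rilonacept, anakinra, canakinumab, methotrexate, azathioprine, cyclosporine, mycophenolate, IVIG = 8.
- Exclusion 17: rilonacept, anakinra, canakinumab, methotrexate, azathioprine, cyclosporine, IVIG = 7.
- Difference: 8 − 7 = 1, mycophenolate. It is missing from all three copies of the criteria, including the SAP's.

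**Step 3: inducers.** The criteria that name specific concomitant medicines are 11 (cannabinoids), 16 and 17. None of the 17 mentions a CYP inducer, so note 3 of Appendix 17.8 describes a criterion that does not exist. Carbamazepine and phenytoin are among the strong CYP3A4 inducers in Appendix 17.7. A patient stable on either can meet every listed criterion and, if the drug continues, is in breach of 6.6 from the first dose. The same holds for mycophenolate.

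**Step 4: where the lists do agree.** The QT bar concerns starting a drug during the study, so it creates no mismatch at enrolment. Criterion 16 is consistent with Section 6.6. Appendix 17.8 gives monitoring advice and does not bar the drugs in its table, so a drug's presence there adds nothing to the conflict.

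**The case against.** The best defence is that the protocol must be read whole. Section 14.4.1 requires its instructions to be followed exactly, and Visit 1 collects current medication and one month of medication history before study treatment is assigned. A careful site would therefore see the 6.6 bars in time. No passage permits an inducer or mycophenolate; the eligibility points are omissions. Exclusion 14 lets a site decline anyone unlikely to comply. Sections 6.6 and 9.2.11.5 also refer to the Investigator Brochure, which is not available here.

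Much of this stands for the eligibility lists. They are mismatches, not permissions, and a careful site can avoid the problem. But criterion 14 names no drug, and it does not make note 3 true or restore the missing agent. The defence does not reach Section 6.8, because reading the whole protocol is exactly what exposes two rules that cannot both be followed.

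A reader might also infer that Section 6.7 contradicts 6.6 by allowing rilonacept as rescue. The documents do not support putting it so strongly. Section 6.7 is a specific rule for recurrence in the extension period, applied after contact with the medical monitor, and it reads naturally as an exception to the general rule. Study drug is not left undefined either: Section 6.5.1 does not list rescue among the reasons for permanent suspension, and Section 8.2 continues the highest tolerated dose to the end of the study. Only a cross-reference is missing.

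**Conclusion.** The inconsistency is real and should be corrected. Its main part is Section 6.8 against the bars in 6.6 and the synopsis, with 9.2.11.5 supporting the QTc bar only. The lesser part is one immunosuppressant missing from exclusion 17 and one appendix note that misdescribes Section 5.3. The breach from the first dose assumes that the patient stays on the barred drug.

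Three stronger readings are tempting and not supported:

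- A reader might take the gaps between scheduled ECGs as the time a QT-active COVID-19 drug could run unobserved. A visit interval is not a treatment duration. The documents give no such duration, and Section 6.8 names no COVID-19 treatment.
- A reader might express the harm as a share of the roughly 25 patients. The documents do not show how many, if any, would be affected.
- A reader might infer that an inducer would distort the exposure results. SAP Section 8.4 derives dose taken from bottle weights, which an inducer does not change, and no drug levels are scheduled.

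No inferential analysis is planned, so no error rate is at stake. The consequences are for patient safety, attribution of events and classification of deviations.

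**What to change.** Reconcile the passages in one protocol amendment, with the sponsor deciding the clinical rule in each case:

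1. In Section 6.8, state whether the prohibitions in Section 6.6 and Appendices 17.6 and 17.7 apply to COVID-19 treatments.
2. Make exclusion 17 and the Section 6.6 list agree on mycophenolate, in the synopsis, Section 5.3 and the SAP's copy.
3. Make Section 5.3 and Appendix 17.8 note 3 agree on strong CYP3A4 inducers.
4. As a minor clarification, cross-refer Sections 6.6 and 6.7 and say whether rescue rilonacept is an exception.

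The cost is wording only, with no new procedure or visit. Depending on how the lists are reconciled, a rare patient's eligibility may change.

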## 7 STUDY PLAN

## 8 INVESTIGATIONAL PRODUCTS, DOSE AND DURATION OF TREATMENT

### 8.1 *Investigational Product*

CardiolRx™ is synthetically produced. It contains cannabidiol oil in a concentration of 100 mg/mL and is free of THC (<5 ppm).

### 8.2 *Administration, Dosage and Duration of Treatment*

Study drug will be administered orally (via syringe) **with food** according to the following treatment schedule:

- Initial starting dose (Day 1 p.m. dose to Day 3 a.m. dose):  
5 mg/kg of body weight CardiolRx™ b.i.d.
- Day 3 p.m. dose to Day 10 a.m. dose:  
7.5 mg/kg of body weight CardiolRx™ b.i.d.
- Day 10 p.m. dose to end of study (a.m. dose at Week 26):  
10.0 mg/kg of body weight CardiolRx™ b.i.d.
- The morning and evening doses should be taken minimally 6 hours and maximally 18 hours between each intake.

If the next higher dose is not tolerated, the patient should return to the last tolerated dose. The highest tolerated dose should be administered until the end of the study (26 weeks post start of study medication).

### 8.3 *Study Treatment Return and Reconciliation*

A detailed treatment dispensing log will be kept at each site, which will be checked at each monitoring visit. After completion of the study, including final drug accountability, all unused study materials must be destroyed on site.

### 8.4 *Supply, Packaging, Labelling and Storage*

#### 8.4.1 Supply and Packaging

The study drug will be provided in 30 mL bottles. New bottles will be supplied for each assessment period.

#### 8.4.2 Labelling and Storage

All investigational drugs will be labeled in English and Spanish according to local regulations for investigational drugs.

All clinical drug supplies are to be stored in a secure, limited-access area as follows:

- Room temperature 59°F - 86°F or refrigerated 36°F - 47°F
- The study supplies need to be protected from light (to be kept in closed cartons or boxes).
- The study supplies need to be stored in an upright position to prevent leakage.

## 9 CONDUCT OF THE STUDY

### 9.1 *Scheduling of Study Procedures*

Patients diagnosed with recurrent pericarditis will be invited to participate in the study. Informed consent must be obtained PRIOR to performing any study-related procedure. There is no time limit between obtaining informed consent and assigning study treatment to the patient. Some of the scheduled follow-up visits may be performed remotely if it's not possible to conduct an in-patient visit. The following must be in place to enable a remote visit to take place:

- The patient is able to obtain an ECG recording, which can immediately be transmitted to the study site
- The patient agrees to go to a local laboratory to have the blood tests planned by protocol performed

#### Visit 1 (Screening and baseline assessments – within 72 hours of Day 1)

The following evaluations will be performed a baseline:

- Written informed consent
- Demographics
- Medical History/Current conditions, including prior CV events and interventions
- Clinical assessment
- Vital signs, including heart rate (HR), blood pressure, body height and weight
- Collect highest NRS pain score within the past 7 days of DAY 1
- 12-lead ECG
- C-SSRS
- Collection of concurrent medication and medication history for the previous 1 month
- Local laboratory assessments, including CRP\*, CBC, AST/ALT, alkaline phosphatase, bilirubin, creatinine/eGFR, INR, pregnancy test (in women with childbearing potential)
- AE and SAE recording after informed consent has been obtained
- Assign study treatment to the patient

\* only if no measurement within 7 days of Day 1 is available

#### ***Start of study medication in the evening of Day 1.***

#### Visit 2 (Day 3 + 2 days) – This visit may be performed as a virtual visit if an in-person visit is not possible as long as the ECG recording can be obtained

The following evaluations will be performed on Day 3 after start of study medication:

- Vital signs, including HR and blood pressure (if visit in person)
- Review/collection of daily diary NRS pain scores, if not submitted electronically to Patient Portal if the patient has completed the questionnaire on paper

- 12-lead ECG 5 hours post morning dose (time window 3.5 – 6 hours); QTc intervals on ECG to be reviewed by site investigator, or designate, who decides if patient can continue study medication. If the visit is done remotely, the patient will record the ECG on a portable device at home or will have the ECG recording performed at a local clinic. The tracings must immediately be transmitted to the site for review.
- Study drug dose increase to 7.5 mg/kg of body weight b.i.d. if patient tolerating starting dose of 5 mg/kg of body weight b.i.d. (If patient did not tolerate the starting dose of 5 mg/kg of body weight b.i.d., the patient will stop the study medication but will continue in the study and follow all assessments until Visit 5 to be included in the safety analyses)
- Study drug accountability
- Recording of changes in concomitant medications
- AE and SAE recording

Visit 3 (Day 10 ± 2 days) – This visit may be performed as a virtual visit if an in-person visit is not possible as long as the ECG recording can be obtained

The following evaluations will be performed on Day 10 after start of study medication:

- Vital signs, including HR and blood pressure (if visit in person)
- Review/collection of daily diary NRS pain scores, if not submitted electronically to Patient Portal if the patient has completed the questionnaire on paper
- Collect highest NRS pain score within the past 7 days
- 12-lead ECG 5 hours post morning dose (time window 3.5 – 6 hours); QTc intervals on ECG to be reviewed by site investigator, or designate, who decides if patient can continue study medication. If the visit is done remotely, the patient will record the ECG on a portable device at home or will have the ECG recording performed at a local clinic. The tracings must immediately be transmitted to the site for review.
- Study drug dose increase to 10 mg/kg of body weight b.i.d. if patient tolerating 7.5 mg/kg of body weight b.i.d. If patient did not tolerate 7.5 mg/kg of body weight b.i.d., patient can return to 5 mg/kg of body weight b.i.d.
- Study drug accountability
- Recording of changes in concomitant medications
- AE and SAE recording

Visit 4 (Week 3 ± 3 days) – This visit may be performed as a virtual visit if an in-person visit is not possible as long as the ECG recording can be obtained and the laboratory assessments can be done by a local laboratory.

The following evaluations will be performed at 2 weeks after start of study medication:

- Clinical assessment (if visit in person)
- Vital signs, including HR and blood pressure (if visit in person)
- Review/collection of daily diary NRS pain scores, if not submitted electronically to Patient Portal if the patient has completed the questionnaire on paper

- Collect highest NRS pain score within the past 7 days
- 12-lead ECG 5 hours post morning dose (time window 3.5 – 6 hours); QTc intervals on ECG to be reviewed by site investigator, or designate, who decides if patient can continue study medication. If the visit is done remotely, the patient will record the ECG on a portable device at home or will have the ECG recording performed at a local clinic. The tracings must immediately be transmitted to the site for review.
- Study drug dose adjustment (if patient did not tolerate 10 mg/kg of body weight b.i.d., patient can return to 7.5 mg/kg of body weight b.i.d.)
- Study drug accountability
- Recording of changes in concomitant medications
- AE and SAE recording
- Local laboratory assessments, including CRP, CBC, AST/ALT, alkaline phosphatase, bilirubin, creatinine/eGFR, INR (if visit not in person, patient needs to go to a local laboratory for blood collection and assessments)

